5.3.7 Concomitant medications

Disulfiram is a substrate of CYP3A4, CYP2A6 and CYP2E1 and an inhibitor CYP2E1, CYP1A2 and CYP2C9, and therefore has potential drug-drug interactions.¹¹⁸ Concomitant medications will be documented on the Case Report Form (CRF) up to day 31. Most of these interactions can be managed clinically, as discussed below.

1. Amprenavir oral solution: Amprenavir oral solution contains propylene glycol and should be avoided when using disulfiram.
2. Benzodiazepines: Disulfiram may inhibit the metabolism of certain benzodiazepines. Close monitoring for increased benzodiazepine effects is recommended.
3. Metronidazole. Metronidazole can have a disulfiram-like effect when administered with alcohol and should not be co-administered with this drug.
4. Ritonavir: The gelatin capsule and liquid formulations of ritonavir contain alcohol. We will avoid the use of these formulations. The new ritonavir formulation has a small alcohol content, and thus co-administered with disulfiram is not contraindicated.
5. Sertraline: The oral concentrate version of this drug contains alcohol. Thus, disulfiram should not be co-administered with this drug.
6. Any drug which contains or may contain alcohol should be avoided.
7. Theophylline Derivatives: Disulfiram may increase the serum concentration of theophylline.
8. Tipranavir: Disulfiram may enhance the adverse effect of tipranavir and should be avoided.

9. Vitamin K Antagonists (e.g., warfarin): Disulfiram may increase the serum concentration of Vitamin K. We will exclude individuals who are receiving warfarin.
10. Isoniazid: We will monitor for any potential side effects of isoniazid as the interactions between this drug and disulfiram are unknown
11. Tricyclic antidepressants (TCAs): We will monitor for any potential side effects of TCAs as the interactions between these drugs and disulfiram are unknown.

5.3.8 Prohibited medications

For study days 1-31, use of medications that are considered standard-of-care at the study site (including antiviral medications available under Emergency Use Authorization) is permitted. Use of other medications with potential anti-SARS-CoV-2 activity, including off-label, expanded access, or investigational agents, should be discussed with the team.

Note: Participants who are hospitalized during the study are eligible to receive COVID-19 treatment per local standard of care, including remdesivir, immunomodulatory agents and/or convalescent sera/plasma and will not be excluded from the study if receiving this standard of care. Azithromycin administered for treatment of presumed or confirmed infection will be permitted.

After study day 31, use of anti-COVID-19 treatments as salvage therapy for those with persistent severe COVID-19 are permitted but should be recorded.

5.4 Study procedures

5.4.1. Figure 1. SCHEDULE OF EVALUATIONS:

	Screen/ Baseline	Day 1 Clinic	Day 2 Clinic	Day 3 Phone	Day 4 Phone	Day 5 Pre dose	Day 5 2-hour Post dose	Day 5 4-hour Post dose	Day 7 Phone	Day 9 Phone	Day 15 Clinic	Day 31 Clinic
Informed Consent	X											
Release of information	X											
Questionnaire		X					X				X	X
Symptom diary/ AE check	X	X	X	X	X		X		X	X	X	X
Vital signs (BP, HR, R, Temp, SP02)	X	X ^a				X ^a	X ^b	X ^b			X	X
Targeted Physical Exam	X	X				X					X	X
SARS-COV-2 PCR TEST	X											
Saliva		X				X ^a					X	X
Complete blood count with differential	X		X ^b			X ^a					X	X
Comprehensive Metabolic Panel	X		X ^b			X ^a					X	X
Erythrocyte Sedimentation Rate (ESR)	X		X ^b			X ^a					X	X
C-Reactive Protein (Inflammation)	X		X ^b			X ^a					X	X
D-Dimer	X		X ^b			X ^a					X	X
Lactate Dehydrogenase (LDH)	X		X ^b			X ^a					X	X

Ferritin	X		X ^b			X ^a					X	X
Urine Pregnancy test (if WOCBP)	X					X ^a						
CD4+/CD8+ T cell counts (if HIV positive)	X											X
HIV RNA-standard Assay (if HIV positive)	X											X
PK Samples			X ^b			X ^a	X ^b	X ^b			X	X
PBMC		X				X ^a	X ^b	X ^b			X	X
Plasma		X				X ^a	X ^b	X ^b			X	X
Serum		X				X ^a	X ^b	X ^b			X	X
NP Swab		X	X ^b			X ^a					X	X
Study Drug/Placebo Administration (Given after blood collection on clinic visit days)		X	X	X	X	X						
• Cohort 1 = (N=20) 1000mg/day; (N=10 placebo)												
• Cohort 2 = (N=20) 2000mg/day; (N=10 placebo)												

a=predose

b=post-dose

The frequent time points are to detect both drug levels and human immune response. Red Cross limits are 500 mL per two months, which we do not exceed in this study. There is no stated guideline for blood volumes for this patient population, so we are utilizing the guidelines from interventional HIV cure trials, when often, serial blood sampling are completed in a single day. The total volume collected at each visit is as follows:

Day 0 Screen/Baseline:	15 mL
Day 1: Pre-Dose	65 mL
Day 2: Post Dose	19 mL
Day 5 Hour -0.5 pre-dose:	59 mL
Day 5 Hour 2 post dose:	45 mL
Day 5 Hour 4 post dose:	45 mL
Day 15:	79 mL
Day 31:	79 mL

The total volume collected during the study is 406 mL and does not exceed the Red Cross limit of 500 mL. Safety labs collected during these visits will be monitored, and volume will be decreased at the discretion of the PI if needed. The blood volumes in this study were carefully calculated to stay within Red Cross Guidelines. This is the approach that is taken in HIV interventional trials, and indeed, the PK sampling days can be tricky. Even for observational (non-interventional trials), there are large volume protocols with separate Informed Consent, for example, the HIV SCOPE cohort that allows a much larger blood draw in a single day for the type of research assays being performed for DISCO. Indeed, most of the whole blood is processed and cryopreserved for several years to be applied towards future assays that have yet to be discovered at this time. In a recent project, 202 HIV+ samples were pulled, that were collected in the 1990s from the SCOPE cohort to be applied to advanced host whole genome sequencing assays that we now have available today.

This trial is not only looking at clinical outcomes. The mechanism by which disulfiram acts is not well understood but based on [name] recent data in Nature Immunology- this drug may have important implications not just for SARS-CoV-2, but other infectious pathogens that trigger an aberrant inflammatory response. If we are going to ask these study participants to take a study drug, we would like to understand HOW it is working, which may point to upstream novel drug targets that may be even more effective down the line in treating COVID-19. Each research assay requires approximately 10 cc of whole blood (Ficolled into PBMCs, peripheral blood mononuclear cells). Some assays require 2 aliquots.

Red Cross Guidelines recommend staying with 480 cc over a 56-day period. We have tried to stay within that in order to draw the minimum samples needed to study host gene expression, host immune cell, PK changes after study drug; this includes changes in genes that are expressed in the hours after taking disulfiram. Although we are drawing this amount of blood in a 31-day period of time, the rationale for this is that in order to study an ACUTE viral illness, the first month of the host response is critical. Drawing blood later after the acute illness has passed makes those latter timepoint blood collections less informative. Moreover, even if the patient continues in clinical care, you can see from the attached blood volumes chart that the clinical lab draws make up a small proportion of the blood draws for these types of translational immunologic studies.

Prior to the DISCO trial, we conducted a pilot study titled COVID-19 Host Immune Response Pathogenesis study (CHIRP) and the amount of blood drawn during the study in 3 weeks was 486 mL. There was no adverse event observed during the study. DISCO trial is designed to enroll patients with mild cases of COVID infection and further understand the immunogenicity of COVID-19 infection.

5.5 Study procedures by day

5.5.1 Screen and Baseline (Day -3 to Day 1)

1. Informed consent (obtained before performing study related activities)
2. Questionnaire Evaluation to include the COVID-19 Index Initial General questionnaire, COVID-19 Index Initial Substance Use, Reproductive Health survey, and Mental Health Supplemental Form
 - Demographics: Age, sex, race
 - Medical history: acute and chronic medical conditions that are risk factors for COVID – e.g., diabetes, cardiovascular disease, chronic obstructive pulmonary disease.
 - Transmission history: timing of exposure to COVID-19 source patient
 - Medications, allergies
 - Any medical condition arising after consent to be recorded as AE
 - Prior COVID-19 testing history (SARS-CoV-2 RT-PCR or antibody): positive test PCR required within 7 days of screening must be documented
 - COVID-19 symptom screen: 5-point ordinal adapted somatic symptom scale (SSS-8)³
3. Targeted physical exam and vital signs (temperature, heart rate, blood pressure, respiratory rate, oxygen saturation by pulse oximetry)
4. Clinical lab collection (run in real-time)
 - a. Screening labs: **complete** blood count with differential, urea, electrolytes, creatinine, calcium, magnesium, phosphate, liver function tests
 - b. Clinical labs associated with severe COVID: erythrocyte sedimentation rate (ESR), high sensitivity C-reactive protein (hs-CRP), D-dimer, lactate dehydrogenase (LDH), and ferritin.
 - c. Clinical labs to confirm COVID+ status: SARS-CoV-2 NP swab PCR assay
 - d. Females of childbearing potential: plasma beta-hCG urine pregnancy test
 - e. HIV+ participants: a CD4+/CD8+ T cell count and standard plasma HIV RNA assay.
5. Samples collected for research (run in batch at end of study enrollment)
 - a. Saliva for host DNA sequencing and potential future SARS-CoV-2 quantification (RNA levels and anti-SARS-CoV-2 IgA)
6. Randomization of those found to be eligible

5.5.2 Study Drug/ Placebo Administration (Day 1)

5.5.2.1 Pre-Dose (Between Hour -0.5 and 0)

1. Questionnaire Evaluation to include the Index Follow up Questionnaire
2. Targeted physical exam and vital signs
3. Clinical lab collection

4. Samples collected for research (storage)
 - a. Blood: PBMC (CyTOF, single cell sequencing), plasma (plasma SARS-CoV-2 viral load), serum (SARS-CoV-2 serology)
 - b. Nasopharyngeal swab for SARS-CoV-2 viral load
 - c. Saliva for host DNA sequencing and potential future SARS-CoV-2 quantification (RNA levels and anti-SARS-CoV-2 IgA)

5.5.2.2 Dose (Hour 0)

Study staff to dispense the first dose of disulfiram or placebo to participant in person. The subsequent doses will be self-administered at home and the time noted as below.

5.5.3 Study Drug/ Placebo Administration (Day 2)

Participant will come to the clinic for clinical laboratory to include complete blood count with differential, urea, electrolytes, creatinine, calcium, magnesium, phosphate, liver function tests, erythrocyte sedimentation rate (ESR), high sensitivity C-reactive protein (hs-CRP), D-dimer, lactate dehydrogenase (LDH), and ferritin, plasma PK testing, and Nasopharyngeal swab for SARS-CoV-2 viral load. Saliva for host DNA sequencing and potential future SARS-CoV-2 quantification (RNA levels and anti-SARS-CoV-2 IgA) will be collected.

The participant will be asked to hold the day 2 study medication until after the blood draw. After the blood has been collected, the participant will be asked to take their day 2 dose of study medication. The time of pre-dose blood draw and the study medication administration date and time will be recorded.

The subject will complete a daily symptom check using the COVID-19 symptom severity questions adapted from the Somatic Symptom Scale (SSS-8) (table 3) while at the clinic and will be assessed for any adverse events.

5.5.4 Study Drug/ Placebo Administration (Day 3)

Participant will self-administer the third dose of disulfiram or placebo at home. The participant will note the time of self-administration and will complete a daily symptom diary. Study coordinator will call patient to verify their symptoms, confirm self-administered dose, and evaluate for any adverse events. If any AEs are reported, an AE form will be completed by the study coordinator, and the PI will be notified for any Grade 3 or above AE.

5.5.5 Study Drug/ Placebo Administration (Day 4)

Participant will self-administer the fourth dose of disulfiram or placebo at home. The participant will note the time of self-administration and will complete a daily symptom diary. Study coordinator will call patient to verify their symptoms, confirm self-administered dose, and evaluate for any adverse events. If any AEs are reported, an AE form will be completed by the study coordinator, and the PI will be notified for any Grade 3 or above AE.

5.5.6 Study Drug/ Placebo Administration (Day 5)

5.5.4.1 Pre-Dose (Hour -0.5 to Hour 0)

1. Questionnaire Evaluation
2. Targeted physical exam and vital signs
3. Clinical lab collection to include;
complete blood count with differential, urea, electrolytes, creatinine, calcium, magnesium, phosphate, liver function tests, erythrocyte sedimentation rate (ESR), high sensitivity C-reactive protein (hs-CRP), D-dimer, lactate dehydrogenase (LDH), and ferritin.
4. Samples collected for research (storage)
 - a. Blood: PBMC (CyTOF, single cell sequencing), plasma (plasma SARS-CoV-2 viral load), serum (SARS-CoV-2 serology)
 - b. Nasopharyngeal swab for SARS-CoV-2 viral load
 - c. Saliva for host DNA sequencing and potential future SARS-CoV-2 quantification (RNA levels and anti-SARS-CoV-2 IgA)

5.5.4.2 Dose (Hour 0)

Study staff to dispense the fifth (last) dose of disulfiram or placebo to the participant.

5.5.4.3 Post-Dose (Hour 2)

1. Samples collected for research (storage)
 - a. Blood: PBMC (CyTOF, single cell sequencing), plasma (PK, plasma SARS-CoV-2 viral load), serum (SARS-CoV-2 serology)

5.5.4.4 Post-Dose (Hour 4)

1. Samples collected for research (storage)
 - a. Blood: PBMC (CyTOF, single cell sequencing), plasma (PK, plasma SARS-CoV-2 viral load), serum (SARS-CoV-2 serology)

5.5.7 Symptom/Adverse Event Telephone Follow-Up (Day 7)

Participant will self-administer a daily symptom/adverse event diary. Study coordinator will call patient to verify their symptoms and evaluate for any adverse events. If any AEs are reported, an AE form will be completed by the study coordinator, and the PI will be notified for any Grade 3 or above AE.

5.5.8 Symptom/Adverse Event Telephone Follow-Up (Day 9)

Participant will self-administer a daily symptom/adverse event diary. Study coordinator will call patient to verify their symptoms and evaluate for any adverse events. If any AEs are reported, an AE form will be completed by the study coordinator, and the PI will be notified for any Grade 3 or above AE.

5.5.9 Symptom/Adverse Event Telephone Follow-Up (Day 11)

Participant will self-administer a daily symptom/adverse event diary. Study coordinator will call patient to verify their symptoms and evaluate for any adverse events. If any AEs are reported, an AE form will be completed by the study coordinator, and the PI will be notified for any Grade 3 or above AE.

5.5.10 Follow-Up (Day 15)

1. Questionnaire Evaluation
2. Targeted physical exam and vital signs
3. Clinical lab collection
 - a. Complete blood count with differential, urea, electrolytes, creatinine, calcium, magnesium, phosphate, liver function tests, erythrocyte sedimentation rate (ESR), high sensitivity C-reactive protein (hs-CRP), D-dimer, lactate dehydrogenase (LDH), and ferritin.
4. Samples collected for research (storage)
 - a. Blood: PBMC (CyTOF, single cell sequencing), plasma (plasma SARS-CoV-2 viral load), serum (SARS-CoV-2 serology)
 - b. Nasopharyngeal swab for SARS-CoV-2 viral load
 - c. Saliva for host DNA sequencing and potential future SARS-CoV-2 quantification (RNA levels and anti-SARS-CoV-2 IgA)

5.5.11 Follow-Up (Day 31)

5. Questionnaire Evaluation
6. Targeted physical exam and vital signs
7. Clinical lab collection
 - a. Complete blood count with differential, urea, electrolytes, creatinine, calcium, magnesium, phosphate, liver function tests, erythrocyte sedimentation rate (ESR), high sensitivity C-reactive protein (hs-CRP), D-dimer, lactate dehydrogenase (LDH), and ferritin.
8. Samples collected for research (storage)
 - a. Blood: PBMC (CyTOF, single cell sequencing), plasma (plasma SARS-CoV-2 viral load), serum (SARS-CoV-2 serology)
 - b. Nasopharyngeal swab for SARS-CoV-2 viral load
 - c. Saliva for host DNA sequencing and potential future SARS-CoV-2 quantification (RNA levels and anti-SARS-CoV-2 IgA)
 - d. HIV+ participants: a CD4+/CD8+ T cell count and standard plasma HIV RNA assay.
9. Samples collected for research (storage)
 - a. Blood: PBMC (CyTOF, single cell sequencing), plasma (plasma SARS-CoV-2 viral load), serum (SARS-CoV-2 serology)
 - b. Nasopharyngeal swab for SARS-CoV-2 viral load

- c. Saliva for host DNA sequencing and potential future SARS-CoV-2 quantification (RNA levels and anti-SARS-CoV-2 IgA)

5.6 Table 3. COVID-19 symptom severity questions adapted from the Somatic Symptom Scale (SSS-8). 3

Symptom	New occurrence or worsening of pre-existing symptom during illness	When did it start? (MMM/DD/YY) If day cannot be estimated within 3 days of true onset, include month and year and mark day not known.	Skip if start date known. Was it present in the first 3 days of illness?	Are you still experiencing it, meaning in the past 2 days? For recovered phase, add: By this we mean that your initial symptoms you had when you first developed COVID-19 have not gone away.	Skip if still experiencing the symptom. How many days did it last? This is defined as start date to last date experienced.	When the symptom was at its worst, how much did it bother you? Please answer on a scale from 1 to 5, where 1 is NONE and 5 is VERY MUCH.
Feeling feverish	 Yes  No	____/____/____  Day not known	 Yes  DK  No	 Yes  No	 Don't know	 1  3  5  2  4
Measured a temperature of >100.4°F or 38°C	 Yes  No	____/____/____  Day not known	 Yes  DK  No	 Yes  No	 Don't know	 1  3  5  2  4
Chills, feeling unusually cold	 Yes  No	____/____/____  Day not known	 Yes  DK  No	 Yes  No	 Don't know	 1  3  5  2  4
Fatigue or feeling tired	 Yes  No	____/____/____  Day not known	 Yes  DK  No	 Yes  No	 Don't know	 1  3  5  2  4
Cough	 Yes  No	____/____/____  Day not known	 Yes  DK  No	 Yes  No	 Don't know	 1  3  5  2  4
Shortness of breath or difficulty breathing	 Yes  No	____/____/____  Day not known	 Yes  DK  No	 Yes  No	 Don't know	 1  3  5  2  4
Chest pain	 Yes  No	____/____/____  Day not known	 Yes  DK  No	 Yes  No	 Don't know	 1  3  5  2  4
Runny nose or congestion	 Yes  No	____/____/____  Day not known	 Yes  DK  No	 Yes  No	 Don't know	 1  3  5  2  4

Symptom	New occurrence or worsening of pre-existing symptom during illness	When did it start? (MMM/DD/YY) If day cannot be estimated within 3 days of true onset, include month and year and mark day not known.	Skip if start date known. Was it present in the first 3 days of illness?	Are you still experiencing it, meaning in the past 2 days? For recovered phase, add: By this we mean that your initial symptoms you had when you first developed COVID-19 have not gone away.	Skip if still experiencing the symptom. How many days did it last? This is defined as start date to last date experienced.	When the symptom was at its worst, how much did it bother you? Please answer on a scale from 1 to 5, where 1 is NONE and 5 is VERY MUCH.
Sore throat	 Yes  No	____/____/____  Day not known	 Yes  DK  No	 Yes  No	 Don't know	 1  3  5  2  4
Muscle aches	 Yes  No	____/____/____  Day not known	 Yes  DK  No	 Yes  No	 Don't know	 1  3  5  2  4
Loss of appetite	 Yes  No	____/____/____  Day not known	 Yes  DK  No	 Yes  No	 Don't know	 1  3  5  2  4
Nausea	 Yes  No	____/____/____  Day not known	 Yes  DK  No	 Yes  No	 Don't know	 1  3  5  2  4
Vomiting	 Yes  No	____/____/____  Day not known	 Yes  DK  No	 Yes  No	 Don't know	 1  3  5  2  4
Abdominal pain	 Yes  No	____/____/____  Day not known	 Yes  DK  No	 Yes  No	 Don't know	 1  3  5  2  4
Diarrhea	 Yes  No	____/____/____  Day not known	 Yes  DK  No	 Yes  No	 Don't know	 1  3  5  2  4
Trouble with smell or taste	 Yes  No	____/____/____  Day not known	 Yes  DK  No	 Yes  No	 Don't know	 1  3  5  2  4

Symptom	New occurrence or worsening of pre-existing symptom during illness	When did it start? (MMM/DD/YY) If day cannot be estimated within 3 days of true onset, include month and year and mark day not known.	Skip if start date known. Was it present in the first 3 days of illness?	Are you still experiencing it, meaning in the past 2 days? For recovered phase, add: By this we mean that your initial symptoms you had when you first developed COVID-19 have not gone away.	Skip if still experiencing the symptom. How many days did it last? This is defined as start date to last date experienced.	When the symptom was at its worst, how much did it bother you? Please answer on a scale from 1 to 5, where 1 is NONE and 5 is VERY MUCH.
New spots or rash on your skin	 Yes  No	_____ / _____ / _____  Day not known	 Yes  DK  No	 Yes  No	 _____  Don't know	 1  2  3  4  5
Trouble concentrating, trouble with your thinking, or trouble with your memory	 Yes  No	_____ / _____ / _____  Day not known	 Yes  DK  No	 Yes  No	 _____  Don't know	 1  2  3  4  5
Headache	 Yes  No	_____ / _____ / _____  Day not known	 Yes  DK  No	 Yes  No	 _____  Don't know	 1  2  3  4  5
Trouble with vision (e.g. double vision, blurry vision, or other visual issues)	 Yes  No	_____ / _____ / _____  Day not known	 Yes  DK  No	 Yes  No	 _____  Don't know	 1  2  3  4  5
Dizziness, feeling like you are spinning, or the world is spinning around you	 Yes  No	_____ / _____ / _____  Day not known	 Yes  DK  No	 Yes  No	 _____  Don't know	 1  2  3  4  5
Trouble with balance or feeling unsteady	 Yes  No	_____ / _____ / _____  Day not known	 Yes  DK  No	 Yes  No	 _____  Don't know	 1  2  3  4  5
Numbness, tingling, or "pins and needles" in your arms or legs	 Yes  No	_____ / _____ / _____  Day not known	 Yes  DK  No	 Yes  No	 _____  Don't know	 1  2  3  4  5
Difficulty falling or staying asleep	 Yes  No	_____ / _____ / _____  _____	 Yes  DK  No	 Yes  No	 _____  Don't know	 1  2  3  4  5

		 Day not known				
Symptom	New occurrence or worsening of pre-existing symptom during illness	When did it start? (MMM/DD/YY) If day cannot be estimated within 3 days of true onset, include month and year and mark day not known.		Are you still experiencing it, meaning in the past 2 days? For recovered phase, add: By this we mean that your initial symptoms you had when you first developed COVID-19 have not gone away.	Skip if still experiencing the symptom. How many days did it last? This is defined as start date to last date experienced.	When the symptom was at its worst, how much did it bother you? Please answer on a scale from 1 to 5, where 1 is NONE and 5 is VERY MUCH.
		 Yes	____ / ____ / ____			
Irritability, agitation, or difficulty controlling your emotions	 No	____ / ____ / ____  Day not known	 No	 Don't know		
Decreased interest in activities or socializing with others	 Yes	____ / ____ / ____	 Yes  DK	 Yes  No	____	 1  3  5  2  4
Use the following instruction table to determine what to ask next based on previous responses.						

Reported symptoms in Q19?	Symptoms uncovered in table above?	Question to ask
Yes	Yes or No	Were there other symptoms that you experienced?  Yes → Go to 23  No → SKIP to 24
No	Yes	I'm glad we went through this list. Do any other symptoms come to mind?  Yes → Go to 23  No → SKIP to 24
No	No	→ SKIP to 26

1. What other symptoms did you experience? Follow the instructions from question 22 for completing each row of the table.						
Other: Specify _____	 Yes  No	____ / ____ / ____  Day not known	 Yes  DK  No	 Yes  No	____	 1  3  5  2  4
Other: Specify _____	 Yes  No	____ / ____ / ____  Day not known	 Yes  DK  No	 Yes  No	____	 1  3  5  2  4

5.7 Table 4. Adverse Event Log form.

DISCO PIDXXXX-04-2021	Adverse Event Log		Subject ID _____	Initials _____
--------------------------	-------------------	--	------------------	----------------

AE #	Adverse Event (diagnosis or symptom)	Dates	Severity	Considered an SAE	Relationship to Investigational drug	Action taken with study drug	Outcome
		Start Date Stop Date	 mild  moderate  severe	 yes  no	 Definitely Related  Probably related  Possibly Related  Unlikely Related  Not related	 none  discontinued  dose adjusted  interrupted  unknown  N/A	 ongoing  ongoing and stable  resolved  resolved with sequelae  unknown  death
	INVESTIGATOR SIGNATURE	 Start Date Stop Date	 mild  moderate  severe	 yes  no	 Definitely Related  Probably related  Possibly Related  Unlikely Related  Not related	 none  discontinued  dose adjusted  interrupted  unknown  N/A	 ongoing  ongoing and stable  resolved  resolved with sequelae  unknown  death
	INVESTIGATOR SIGNATURE	 Start Date Stop Date	 mild  moderate  severe	 yes  no	 Definitely Related  Probably related  Possibly Related  Unlikely Related  Not related	 none  discontinued  dose adjusted  interrupted  unknown  N/A	 ongoing  ongoing and stable  resolved  resolved with sequelae  unknown  death
	INVESTIGATOR SIGNATURE	 Start Date Stop Date	 mild  moderate  severe	 yes  no	 Definitely Related  Probably related  Possibly Related  Unlikely Related  Not related	 none  discontinued  dose adjusted  interrupted  unknown  N/A	 ongoing  ongoing and stable  resolved  resolved with sequelae  unknown  death

I attest that the above information has been reviewed and is true and accurate

Principal Investigator Signature

Date

Adverse Event Log Page _____ of _____

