SECONDARY ENDPOINTS	
 • Safety and tolerability • Change in SARS-CoV-2 PCR quantitative viral load⁴ at days 5, 15, and 31. • Change in COVID-19 clinical stage (five-point symptom severity scale³) at days 5, 15, and 31. • Time to recovery (date of symptom onset to date of complete resolution of symptoms) • If applicable, the proportion of participants hospitalized at day 5, 15, and 31. • If applicable, the proportion of participant deaths at day 5, 15, and 31
OTHER EVALUATIONS	
 • SARS-CoV-2 specific T- and B- cell responses⁵ • Pyroptosis (aberrant proinflammatory cell death) assay⁶ • High sensitivity SARS-CoV-2 antibody titer (IgM, IgE, IgA, IgG1, IgG2, IgG3, IgG4) • Changes in host gene and protein expression from matched blood and respiratory (NP) samples at the single cell level (B, T, natural killer, and myeloid cells). • Changes in T- and B-cell receptor (TCR/BCR) repertoire from matched blood and respiratory (nasal/oropharyngeal) samples.
SAFETY EVALUATIONS	All participants will be followed for possible adverse events (AEs) throughout their involvement in the study.
PLANNED INTERIM ANALYSES	A Safety Monitoring Committee (SMC) will be convened and will meet biannually to review all adverse events and the conduct of the study. Serious adverse events will be monitored by the committee on an ongoing basis throughout the study. All main analyses will be conducted on an intention-to-treat basis. Models will assess the relationship between the timing of disulfiram treatment initiation relative to symptom onset and study outcomes for key efficacy/activity endpoints. Stratified analyses will be performed based on symptom severity, as well as laboratory values (e.g., hs-CRP, ferritin, D-dimer levels at baseline).

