From the time to treatment initiation to clinical recovery or improvement, all participants will be censored at the end of follow-up, not at the time of event (e.g., for mortality). Sensitivity analyses will be performed using imputation of missing data to differentiate discontinuation of participants from treatment versus study evaluations.

Duration of fever, duration of symptoms and duration of time to self-reported return to usual health will be summarized with descriptive statistics. Participant-specific durations of fever and symptoms will be compared between study arms using a two-sided stratified Wilcoxon test with a 5% Type I error rate. Total symptom score will be calculated on each day and the participant-specific area under the curve (AUC) over time will also be compared using a two-sided stratified Wilcoxon test. Participants who do not have complete diary cards due to hospitalization or death will be ranked in these analyses as having poorer outcomes than participants who survived without hospitalization.

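### Table 3 opens a symptom row on worsening of a pre-existing symptom but has no return-to-usual option for closing it, so a settled chronic symptom can block recorded recovery

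*Combined protocol and SAP*

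**What the plan says.** **Opening a row.** Section 5.6, Table 3, lists 26 named symptoms. The first column of each row asks about "New occurrence or worsening of pre-existing symptom during illness".

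**Closing a row.** The form then asks "Are you still experiencing it, meaning in the past 2 days". For the recovered phase it adds "By this we mean that your initial symptoms you had when you first developed COVID-19 have not gone away". If the answer is no, the participant gives the number of days it lasted: "This is defined as start date to last date experienced". If the answer is yes, the duration item is skipped.

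**Severity.** The 1 to 5 rating asks "When the symptom was at its worst, how much did it bother you". It records neither the pre-illness level nor the current level.

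**Outcomes that depend on symptoms ending.** The synopsis lists among the secondary endpoints "Time to recovery (date of symptom onset to date of complete resolution of symptoms". Section 6.2 states: "Participant-specific durations of fever and symptoms will be compared between study arms using a two-sided stratified Wilcoxon test", at a 5% type I error. The same paragraph lists the time to self-reported usual health, but only for descriptive summary.

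**The concern.** The opening question is relative: it compares the symptom with what the participant had before. The closing question is absolute: it asks whether the symptom is there at all. For a new symptom the two agree. For a worsened pre-existing symptom they do not, because such a symptom normally ends by returning to its usual level.

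Many of the 26 items are commonly chronic, such as fatigue, cough, headache, numbness, poor sleep and loss of interest. Section 5.5.1 records chronic conditions at baseline, including chronic obstructive pulmonary disease, and section 5.3.2 does not exclude that disease by name. One such item is enough to prevent complete resolution.

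At stake are time to recovery and the between-arm comparison of symptom duration. People who are back to normal may be recorded as still ill, in both arms. With 10 placebo participants per cohort, a chance imbalance in chronic symptoms also carries weight.

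**Working it through.** The plan gives no power or sample-size figure for recovery or symptom duration, so there is no figure to reproduce. The check is first textual, then illustrative.

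**1. The rules side by side**

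| Step | New symptom, now gone | Pre-existing symptom, worsened, now at usual level and present daily |
|---|---|---|
| Row opened? | Yes | Yes |
| Felt in past 2 days? | No | Yes |
| Recovered-phase prompt: "your initial symptoms you had when you first developed COVID-19 have not gone away"? | Gone | Not gone, on the literal reading |
| Duration recorded? | Yes | Skipped |
| Complete resolution? | Possible | Blocked |

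No column in the table as shown records the usual level or a return to it. The start-date column also does not say whether it wants the start of the symptom or of the worsening.

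**2. Cap on recovery**

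Let q be the share of participants with a worsened pre-existing symptom that settles but stays present to Day 31 and is answered literally. The documents do not give q; I take 10% to 30% as an assumed range. At most 1 − q can be recorded as recovered: 90%, 80% and 70%. In a cohort of 30 (section 5.3.4) that leaves 3, 6 and 9 people who cannot reach the endpoint.

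With an assumed placebo median of 8 days and exponential recovery, true recovery by 30 days is 1 − 2^(−30/8) = 92.6%. Recorded recovery is 0.926 × (1 − q):

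- q = 10%: 83.3%
- q = 20%: 74.1%
- q = 30%: 64.8%

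One affected person moves the recorded proportion by 1/10 = 10 points in a placebo group and 1/20 = 5 points in an active group.

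**3. Illustrative power**

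Setting: one cohort, 20 v 10; exponential recovery rounded up to whole days; placebo median 8 days; 30 days of follow-up; a random share q in both arms never recorded as recovered; everyone unrecovered tied at the worst rank; two-sided unstratified Wilcoxon test at 0.05. Only the arm sizes, the follow-up length, the type of test and its level come from the documents. Approximate power:

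| Assumed rate ratio | q = 0 | 10% | 20% | 30% |
|---|---|---|---|---|
| 3 | 65% | 42% | 30% | 20% |
| 2 | 31% | 21% | 16% | 10% |

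Repeat runs of 2,000 to 4,000 replicates move individual entries by up to about 4 points.

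A formula that only removes events gives a milder loss. With all 60 participants and a rate ratio of 2.0, power goes from 71.6% at q = 0 to 56.3% at q = 30%. That formula holds the rate ratio at 2.0, whereas participants who cannot recover stay at risk throughout and pull the observed ratio toward 1. It therefore understates the loss.

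**The case against.** **The wording is ambiguous.** 'It' in the closing question could mean the COVID-related worsening, which is over once the usual level returns. This stands as far as it goes: the form contains no explicit rule that a settled chronic symptom counts as illness. But the duration item speaks of the symptom and the recovered-phase prompt speaks of its going away. If two readings are open, participants and coordinators will use both.

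**A reader might infer that such participants are never scored as recovered.** The documents do not support that. An intermittent symptom absent for 2 days closes its row. No section gives the algorithm that turns Table 3 answers into a recovery date. Table 3 also refers to numbered questions that are not shown, so a return-to-usual item elsewhere cannot be ruled out.

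**The plan already has a return-to-usual measure.** Section 6.2 does list one, and it would count these participants. It is planned for description only, and no item shown in Table 3 collects it. It does not correct the symptom durations that are tested.

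**A reader might infer that ongoing symptoms rank worst, or that a log-rank test suffers.** Neither is in the plan. Section 6.2 gives poorer ranks only to diaries left incomplete by hospitalization or death, and it names no log-rank test. Worst-rank scoring is my assumption and drives the loss in the table.

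**The effect is limited.** This stands. Misclassification is balanced in expectation under blinded randomization, and section 6.2 calls the study exploratory. At a rate ratio of 1.5 power is about 14% even with a perfect form, so there is little to lose.

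**Conclusion.** The mismatch is real on the literal wording. Rows open on worsening but close only on absence, and recovery requires complete resolution. A persistent chronic symptom back at its usual level therefore leaves a row without an end date and blocks recovery. This understates recovery and adds noise to time to recovery and symptom duration. It is not expected to favour either arm, and it does not touch the primary cytokine endpoint in section 6.2.1.

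The firm quantitative statement is the cap: recorded recovery cannot exceed 1 − q. The power figures are illustration only. They rest on an assumed q, placebo median, rate ratio and ranking of ongoing symptoms, none of which the documents state. The point is worth correcting because the date of return to usual cannot be reconstructed later from the Table 3 columns if it was not asked.

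**What to change.** For Table 3 rows opened as worsening of a pre-existing symptom:

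- Replace the closing question with: *still worse than your usual level before COVID-19, in the past 2 days?*
- Record the date of worsening as the start and the date back to usual as the end.

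In the synopsis and section 6.2, define complete resolution as every Table 3 symptom absent or back to its pre-COVID-19 level, and use that definition for both time to recovery and symptom duration.

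The cost is a reworded form column, the matching dates, and one sentence in the endpoint definition; no visits are added. The drawback is that the usual level is judged by the participant, though equally in both blinded arms.
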